### 5.5.6 Baseline Characteristics

Baseline characteristics that will be evaluated include patient characteristics, as well as diagnosis (including IV LCM exposure indications and preexisting conditions of interest as described in Section 5.5.3), procedures, and medications administered, dispensed or prescribed (AEDs, benzodiazepines and non-AEDs) (including AED line of therapy) will be evaluated. Diagnostic and procedural data will be identified using International Classification of Disease (ICD)-9, ICD-

10-Procedures, Current Procedural Terminology (CPT)-4, Healthcare Common Procedure Coding System (HCPCS), and Logistical Observation Identifier Names and Codes (LOINC) vocabularies which provide a systematic nomenclature for medical laboratory observations.

## 5.6 Data source and data management

### 5.6.1 Description of database

PEDSnet (pedsnet.org) is a clinical research network (CRN) that was launched in 2014 and is currently a Clinical Data Research Network (CDRN) in member of the Patient-Centered Clinical Research Network (PCORnet, pcor.net). PEDSnet includes 8 pediatric health systems across the United States including Boston Children’s hospital, Children’s Hospital Colorado, Children’s Hospital of Philadelphia, Cincinnati Children’s Hospital Medical Center, Nationwide Children’s Hospital, Nemours Children’s Health System, St Louis Children’s Hospital and Seattle Children’s Hospital. The PEDSnet core data includes information on 6.2 million children, seen since 2009. The regional catchment area for the network extends across 22 states in the US, currently providing care annually for 2.5 million patients, or 2.8% of all children in the USA, from diverse demographic, geographic, and socioeconomic backgrounds. The historical database from 2009-present includes 6.5 million children inclusive of all their inpatient and outpatient care that occurs in member institutions.

The PEDSnet database consists of data from electronic healthcare records (EHRs) generated during a health encounter at any of the health institutions included in the network. The data includes demographic characteristics, encounter data for primary care, specialty care, emergency department and inpatient visits, procedures, prescribed or dispensed medications, laboratory results, diagnoses, anthropometrics and vital signs collected during routine care or management of complex illnesses, [Table 4 Measures available in the PEDSnet database](#).

**Table 4 Measures available in the PEDSnet database**

Domain	Type of Data
Demographics	Age, date of birth, gestational age, sex, ethnicity, race, zip code, PEDSnet health system site, primary care provider, death and cause of death (if available)
Outpatient encounters (~75 visit specialty types available)	Primary care visits, specialty care clinics (e.g., cardiology, endocrinology, nephrology, oncology, etc.), physical therapy, occupational therapy, speech language pathology, medical genetics/genomics, etc.
Inpatient admissions	Length of stay, discharge status; diagnoses, procedures, medications, and lab results associated with inpatient stay
Emergency department encounters	Diagnoses, procedures, medications, and lab results associated with emergency department visit; emergency department visits resulting in inpatient admission
Anthropometrics	Height (cm) and weight (kg), body mass index, head circumference
Vital signs	Temperature, blood pressure
Providers	Specialty, health care facility
Diagnoses	Final diagnoses are recorded at each encounter and are mapped to a standardized codes (typically SNOMED-CT)

Domain	Type of Data
Procedures	Procedures are recorded at each encounter and are mapped to standardized SNOMED-CT, ICD-9 Procedure, ICD-10 Procedure, CPT-4, and HCPCS codes
Prescribed medications	Medications ordered are recorded at each encounter and mapped to a standardized RxNorm code
Dispensed medications	Medications dispensed, when available, are recorded and mapped to a standardized RxNorm code
Laboratory test results	Contains the orders and results for more than 400 laboratory tests. Examples include key components of lipid panel, complete metabolic panel, complete blood counts, microbiologic cultures, liver function tests, urinalysis, viral panels, etc.
Visit payer	Plan class (private/commercial, medicaid/sCHIP, Medicare, other public, self-pay, other/unknown), plan type (HMO, PPO, POS, fee for service, other/unknown) for every unique visit. Enrollment information unavailable.

The EHR contain data in a structured format from predefined categories based on the EHR systems and data in unstructured (free text) format generated from physician and nurses notes. It is anticipated that there may be variation in the amount of clinical data recorded based on the healthcare setting i.e. inpatient, emergency department versus outpatient. It is anticipated that inpatient data will be highly detailed, as complete data capture on all signs and symptoms over the time period spent in hospital is often the practice.

Each of the partner site creates a local dataset. The PEDSnet database is updated on a quarterly basis by extracting data from the member institutions and transforming the data into a CDM. Data are extracted from the EHR and entered into the Research Electronic Data Capture (REDCap) system which enables integration with the structured data captured in a pediatric-specific CDM. The PEDSnet CDM is an extension of the Observational Health Data Sciences and Informatics Collaborative's Observational Medical Outcomes Partnership (OMOP) CDM. It was developed to facilitate the use of data generated from multiple facilities with different EHR structures. PEDSnet uses SNOMED-CT to represent the diagnoses; SNOMED-CT, ICD-9, ICD-10, CPT-4 and HCPCS codes to map procedures; RxNorm for dispensed and prescribed medications; and LOINC to represent laboratory results observations. Each patient is assigned a study code that is used in place of direct identifiers to facilitate longitudinal research with reduced risk of violating privacy. Additionally, each member site operates under the guidance of their Institutional Review Board, which is charged with protecting the safety and privacy of patients and families that participate in research.

## **5.7 Data management and Quality control**

### **5.7.1 Data Quality**

The completeness and validity of the EHRs at the partner sites is dependent upon the physician recording the information during the health encounter. Each PEDSnet institution employs rules relating to how EHR data should be documented to ensure the validity and consistency of the data entered. Quality control of the PEDSnet CDM is ensured by means of an extensive data quality assessment program (DQA) which examines data submitted by each organization and

across all PEDSnet data partners. This program maximizes the validity of the EHR-derived datasets and data quality by means of quarterly extensive data quality testing, which evaluates errors in the collection or standardization of data (i.e. to ensure data is in a “workable” state for research purposes). The process begins with approximately 850 tests done on data from each PEDSnet site in each quarterly data cycle. The errors evaluated by the data coordinating center include programming pipeline errors, data entry errors, administrative errors, or source data incompleteness. The quality assessment includes review of individual data elements for consistency with the CDM specification and with clinical plausibility, for trends over time, and for expected correlations between data elements. The DQA process assesses the description of the operating characteristics of the data in several dimensions which includes data reliability, consistency, accuracy and completeness. Test results are reviewed by data scientists at Data Coordinating Center and discussed with each site. Issues that arise from errors in data extraction or transmission are corrected and the data reloaded. Any identified issues (e.g. errors in data extraction/transmission) can then be resolved. In addition to this, PCORnet conducts a data characterisation process based on the Mini-Sentinel data quality review process. As a PCORnet network partner, PEDSnet must also meet PCORnets coordinating center quality assessments, which further assesses the data model conformance, missing data in enrollment, encounters, demographics, vital findings, diagnoses, and procedures tables, and the plausibility of date and vital measures data.

**Quality assurance:** For the overall data network, data quality assessment (DQA) occurs on several levels. There is a published specification document (current version available at [https://PEDSnet.org/documents/206/ETL\\_Conventions\\_for\\_use\\_with\\_PEDSnet\\_CDM\\_v3.1\\_O\\_MOP\\_V5.2.pdf](https://PEDSnet.org/documents/206/ETL_Conventions_for_use_with_PEDSnet_CDM_v3.1_O_MOP_V5.2.pdf)) that each site uses to develop ETL. The database uses a relational architecture, so the second step applies at data loading, and enforces base type constraints and referential integrity. A series of DQA tests are applied across the entirety of the data, which focus on value set compliance, consistency, missingness, and similar structural checks. The tools are available at <https://github.com/PEDSnet/Data-Quality-Analysis>. There is a summary of experience here:

Relevant data quality issues are included as part of project reporting. During project execution, study-specific DQA may involve several techniques, depending on study design. Routine assessments include areas such as missing data and coding variation across data sources, as well as anomaly detection. Code set development addresses terminology structure, usage patterns, and where possible recovery of missing codes via source values. Cohort DQA includes assessment of variation across subsets, reliability over time, and where external data exist to set expectations, alignment of study data to those expectations. In appropriate studies construct composite measures of data quality across multiple covariates (e.g. different medication exposure variables), have been used as a tool to identify outliers among data sources.

Specification for this type of study-specific DQA is part of the analysis planning that goes on between the requestor’s study team and the data science team here. Finally, where external validation of classification is needed, medical records review is available, whether for a sample of the cohort to establish performance characteristics of an algorithm, or for study-specific data capture where needed. When review is done, a common abstraction tool is used, and post-review adjudication is centrally performed, and reviewers receive common training. We do not

routinely use multiple reviewers per record, though it is an option; routine QA would include inter-rater reliability.

Previous studies have applied these quality assessments to the standard to provide data for FDA submission, and deidentified datasets can be provided to the regulator.

### **5.7.2 Data Validity**

The study will use both the PEDSnet CDM and EHR medical charts data. The validity of the data depends on the source data that was recorded by the physician during each specific encounter. As indicated in the Section 5.7.1, PEDSnet has put in place extensive measures to ensure high validity of the data that is transferred into the CDM. For the chart review, a random sample consisting of 10% of all the EHR medical charts included in the study will be reviewed by a second reviewer and assessed for inter-person variability.

### **5.7.3 Database entry and reconciliation**

The data from the medical chart review will be entered into a validated electronic database using a clinical data management system (CDMS). Computerized data cleaning checks will be used in addition to manual review in order to check for discrepancies and to ensure consistency of the data. An electronic audit trail system will be maintained within the CDMS to track all data changes in the database once the data have been electronically loaded. Regular backups of the electronic data will be performed.

### **5.8 Archiving and Data Retention**

UCB requires the documents to be retained at least for 5 years after completion of the study. The documents should be retained for a longer period, however, if required by the applicable regulatory requirement(s) or by an agreement with UCB.

PEDSnet will contact UCB prior to the destruction of any study records or in the event of accidental loss or destruction of any study records.

### **5.9 Statistics**

For the baseline characteristics, mean, standard deviation, median, and quartiles will be used to describe continuous variables, whereas frequencies and percentages will be used to describe categorical variables. The baseline characteristics will include demographic characteristics, number of previous and concomitant AEDs, and concomitant medications prescribed prior to the index date, prevalence of comorbidities, preexisting medical events of interest, medical procedures such as EEG, and dosage of IV LCM.

All analyses will be stratified as follows:

- Exposure to additional AEDs
- IV LCM treatment indication
- Preexisting medical events of interest
- Use in the intensive care unit or other hospital departments (e.g. emergency department, inpatient, and outpatient setting)

- First time IV loading dose exposure vs previous treatment with index medication

### 5.9.1 Planned analysis

A table of baseline characteristics comparing treatment groups will be presented along with a sub-table of those from each group with SE. Results will be presented stratified by ageband where appropriate.

#### 5.9.1.1 Adjustment for baseline characteristics using propensity scores

We will use propensity score and inverse probability of treatment weights (IPTW) to control confounding (Brookhart 2013). The propensity score will be estimated using a logistic regression model, in which higher IV LCM dose (vs. recommended initial/maintenance IV LCM dose) will be regressed on the baseline characteristics. Covariates for inclusion in the propensity score model were selected based on their potential association with the outcomes, including patient characteristics, patient disease history, and treatment history, as indicated on page 35 of the study protocol under section 5.6.6, and on page 21 section 5.6.3 of the protocol, and as listed below:

- Weight
- Sex
- Age at time of seizure treated with loading dose
- Ethnicity (if available)
- PEDSNet site
- Diagnosed medical conditions
- Prior AED/benzodiazepine prescribing (home use) or administration in hospital
- Prior seizure number if available
- Treatment for said seizures (AED and/or benzodiazepine)
- Concomitant prescribing
- Pre-existing medical conditions of interest for the safety evaluation: cardiac conditions, dermatologic conditions, vascular conditions, injury, poisoning and procedural complications, general disorders and administration site conditions, investigations, drug reaction with eosinophilia and systemic symptoms syndrome, severe cutaneous adverse reactions, hypersensitivity events
- Prior EEG data at last seizure

After the propensity scores have been generated, we will assess for violations of underlying assumptions. Positivity violations will be assessed by plotting the propensity score distributions in an overlay plot for the comparator groups. To evaluate adequate overlap of the propensity scores, we will visually inspect the density distribution of the propensity scores (Rosenbaum and Rubin, 1984). The performance of the model will be evaluated by assessing the covariate balance across the treatment groups. Standardized differences will be used to compare the mean or prevalence of baseline covariates between the comparator treatment groups in the samples

weighted by the inverse probability of treatment. Additionally, continuous variables will be compared using graphical methods including boxplots and nonparametric density plots.

Then we will compute inverse probability of treatment weights, defined as the reciprocal of the probability of receiving the treatment that was actually received using the derived propensity score, to create a pseudo-population where the measured covariates are not associated with the outcome, and both cohorts are standardized to the overall population (Brookhart et al, 2013). Given IPTW is often hampered by extreme propensity scores, resulting in biased estimates and excessive variance, we will evaluate the distribution of the stabilized weights using graphical displays (e.g. boxplots) and descriptive statistics. The characteristics of the patients with outlier weights will be examined and if necessary, the model will be re-specified and the weights re-estimated, or if the outlier are not significant, symmetric trimming methods will be used to exclude these patients using  $\alpha = 0.1$  (cite Crump RK, Hotz VJ, Imbens GW, et al. Dealing with limited overlap in estimation of average treatment effects. *Biometrika*. 2009;96(1):187–199 ).

IPTW-weighted Poisson regression model with robust variance estimator (regressed on exposure status in the sample weighted by the IPTW) will be used to estimate adjusted incidence rate ratios and 95% CIs of each outcome. The advantages of IPTW weighting includes retention all study patients and estimation of an average exposure effect in the whole population of eligible patients as incidence rate ratio (IRR) the other propensity score methods require exclusion of patients who cannot be matched to a control. As this study is reliant on a relatively small population of pediatric patients, and where comparison is undertaken between groups, retaining all patients allows for greater power to investigate significant differences between groups. Use of an alternative matching method would also mean that the effect estimate obtained from the matching would only be generalizable to populations similar to the matched patients. Retention of all patients allows for greater generalizability to background populations.

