### 5.2.5 Dosing criteria for groups

Once the LCM population is identified dose thresholds are applied to define the “Recommended Dose Group” and the “Loading Dose Group”). The following thresholds apply:

The recommended loading dose groups are as follows:

- $< 4$  mg/kg for patients less than 30 kg and less than 6 months of age
- $< 6$  mg/kg for patients less than 30 kg and greater than or equal to 6 months of age
- $< 4$  mg/kg for patients between 30 and 50 kg
- $< 200$  mg for patients
- greater than 50 kg

Note: Whilst babies are allowed higher mg/kg dosing than older children, due to issues of metabolism and weight, babies under 6 months of age have immature organs and a loading dose should be lower than older babies under 1 year.

High dose group have doses greater than the recommended group cut limits, applicable for age and weight.

- $\geq 4$  mg/kg for patients less than 30 kg and less than 6 months of age
- $\geq 6$  mg/kg for patients less than 30 kg and greater than or equal to 6 months of age
- $\geq 4$  mg/kg for patients between 30 and 50 kg
- $\geq 200$  mg for patients greater than 50 kg

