### **5.9.1.3 Analysis of loading dose / higher than recommended initial IV LCM dose**

To examine safety and tolerability of iv LCM administration, the analysis of the key primary and secondary variables will be stratified by loading dose and recommended dose groups, stratified by ageband ie, separate tables per age band. Risk estimates will be provided with incidence rate ratios and 95% confidence limits.

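### The high-dose cut-off steps from 4 to 6 and back to 4 mg/kg across age/weight bands, but the propensity covariate list omits the band, so weighting can leave young infants unbalanced between the arms

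*Protocol*

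**What the plan says.** Protocol section 5.2.5 sets the group boundary by band: 4 "mg/kg for patients less than 30 kg and less than 6 months of age", 6 "mg/kg for patients less than 30 kg and greater than or equal to 6 months of age", 4 "mg/kg for patients between 30 and 50 kg", and an absolute 200 mg above 50 kg. It adds: "High dose group have doses greater than the recommended group cut limits, applicable for age and weight".

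Section 5.9.1.1 plans a logistic propensity model in which "higher IV LCM dose (vs. recommended initial/maintenance IV LCM dose) will be regressed on the baseline characteristics". Its covariate list includes weight and age. It gives no functional form or interaction for either, and it does not list the dose band. The outcome model (5.9.1.1 and 5.9.1.5) is a weighted Poisson regression on exposure alone, so the weights carry all the adjustment.

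On balance, the same section says: "Standardized differences will be used to compare the mean or prevalence of baseline covariates between the comparator treatment groups in the samples", meaning the weighted samples, and adds boxplots and density plots for continuous variables. It mentions re-specifying the model only when discussing outlier weights. Section 5.9.1.3 promises results "stratified by ageband ie, separate tables per age band" but does not define the age bands.

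**The concern.** Group membership is partly decided by the band. A first dose of 5 mg/kg is high at 5 months, recommended at 7 months (under 30 kg), and high again at 31 kg. If prescribing does not follow the same steps, the probability of being in the high group drops at 6 months and rises again at 30 kg because of the grouping rule itself. A propensity model with simple linear age and weight terms has nothing that can follow that pattern.

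The weighted arms could then differ in their share of young infants while mean age and mean weight agree. Any listed event whose background rate differs between young infants and older children would show an incidence rate ratio away from 1 with no dose effect.

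**Working it through.** The protocol gives no power, balance or event-rate figure to reproduce. The 875 in section 5.9.3 is a feasibility count. The check is therefore a simulation of the stated plan under assumptions.

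**From the protocol:** the 5.2.5 cut-offs; a logistic propensity score; weight = 1/P(treatment received); exposure only in the outcome model.

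**Assumed:** infants under 6 months are 5, 10 or 20% of the cohort; other ages uniform to 17 years; a simple weight-for-age curve with log-SD 0.18; first dose lognormal in mg/kg with median m and log-SD s, capped at 400 mg. The central case has 10% infants and m = 5.

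**Step 1, shape of the cut-off.** In mg/kg it runs 4, 6, 4, then 200/weight. At 50 kg, 4 × 50 = 200 mg, so there is no jump there. The jumps are at 6 months and at 30 kg.

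**Step 2, probability of being high when dosing ignores the band.** P(high) = Φ(ln(m/c)/s) for cut-off c, with m = 5:

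| s | c = 4 | c = 6 |
|---|---|---|
| 0.5 | Φ(0.446) = 0.67 | Φ(−0.365) = 0.36 |
| 0.3 | Φ(0.744) = 0.77 | Φ(−0.608) = 0.27 |

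Above 50 kg the simulated values are 0.78 (s = 0.5) and 0.89 (s = 0.3). So the probability is high, then low, then high again.

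**Step 3, weighting with linear age and weight (central case).** After 6 months the probability rises with size, so the linear fit gives infants too low a probability. Infants in the high arm then get weights that are too large.

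| s | Infants, weighted high arm | Infants, weighted comparator | Ratio |
|---|---|---|---|
| 0.3 | 23.5% | 3.5% | 23.5/3.5 = 6.7 |
| 0.5 | 17.2% | 5.4% | 17.2/5.4 = 3.2 |

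For s = 0.3 the unweighted ratio was 2.7, so weighting made the imbalance worse. The weighted standardized differences were 0.03 for mean age and 0.05 for mean weight, but 0.61 for being under 6 months. At N = 875 the median ratio was 6.6 (5th to 95th percentile 4.9 to 10.2) for s = 0.3 and 3.2 (2.5 to 4.5) for s = 0.5. Across the assumed scenarios the ratio ran from about 2 to 13.

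**Step 4, where it shrinks.**
- Linear plus log terms for age and weight: about 1.1 to 2.
- Linear terms, doses proportional to the cut-offs at every age and weight: 0.98 to 1.01.
- Linear terms, infant median 3 against 5 mg/kg in older children: about 1.1.
- Intermediate patterns with linear terms: 1.35 to 1.7 when only infant doses are scaled to the cut-offs, and 1.9 to 3.0 for infant median 4 against 5 mg/kg.

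**Step 5, effect on the incidence rate ratio with no dose effect.** If infants have k times the rate of other children, spurious IRR = (1 + (k−1)p_high)/(1 + (k−1)p_comp), where p is the weighted infant share.
- k = 3, s = 0.3: 1.470/1.070 = 1.37.
- k = 3, s = 0.5: 1.344/1.108 = 1.21.
- k = 0.5, s = 0.3: 0.8825/0.9825 = 0.90.

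Across scenarios with linear terms and band-independent dosing, k = 3 gives about 1.1 to 1.45. If instead all children under 30 kg carry two- or three-fold rates, the spurious ratio is 0.91 to 0.96.

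**Step 6, band added as a factor.** The weighted infant ratio becomes 0.96 to 1.00, with an absolute standardized difference of at most 0.013.

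**The case against.** The band is a deterministic function of two listed covariates, so age and weight are not left unadjusted. Section 5.9.1.1 does not say the terms are linear, and functional form is commonly left to a statistical analysis plan, which may exist. This stands, and it is why the point is conditional. But the protocol itself fixes both the grouping rule and the covariate list, and the list leaves out the variable that sets the boundary.

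A reader might infer that the imbalance arises whatever the prescribing pattern. The documents do not support that. They give no dose distribution, the note in 5.2.5 itself expects lower loading doses under 6 months, and the effect nearly vanishes when dosing tracks the cut-offs.

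A reader might also infer that the bias always inflates the high-dose rate. No age-specific event rates are given. Several listed events, such as dizziness, palpitations and gait disturbance, could plausibly be recorded less often in infants.

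The planned density plots, and age tables if a boundary falls at 6 months, could reveal the problem. No action is tied to either, and the tables leave the pooled estimate unchanged. Mean-based differences can also be visibly off at more extreme dose medians, so the check would not always miss it. Trimming at 0.1 left a ratio of 5.6 to 9.7 in the runs where it was applied.

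**Conclusion.** The point holds in conditional form. With linear age and weight and mg/kg dosing that ignores the bands, the planned weighting can leave children under 6 months about 2- to 13-fold over-represented in the high-dose arm, and in the central case the mean-based balance check would pass. With linear plus log terms the ratio is about 1.1 to 2. With linear terms and dosing that tracked the cut-offs throughout, or was clearly lower in infants, it is about 1.0 to 1.1; partial tracking falls in between.

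The spurious incidence rate ratio of about 1.1 to 1.45 rests on an assumed three-fold infant rate, and other rate patterns reverse its direction. The age mix, dose distribution and event rates are all assumptions. A flat statement that infants will be several-fold over-represented is not supported. This is a worthwhile, cheap improvement to the covariate list. It says nothing about which dose cut-off is right.

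**What to change.** In section 5.9.1.1, add the four-level age/weight dose band of 5.2.5 to the propensity model as a categorical covariate, keeping age and weight. Report the weighted standardized difference for each band in the balance table, and state that the model will be re-specified if a band is unbalanced, whether or not weights are outlying.

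The cost is 3 degrees of freedom for a variable already derived for grouping, four extra rows in the balance table, and somewhat more variable weights if a band is sparse in one group. That last cost is real, because section 5.9.3 expects only several hundred patients. For the same reason, re-estimating the weights separately within each age band is not recommended.
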